6.1 Study treatment

The investigational or study drug to be used in the course of this trial is BGJ398 oral formulation.

Novartis Drug Supply Management or its designee will provide BGJ398 as 100-mg and 25-mg hard gelatin capsules as individual patient supply, packaged in bottles or blisters. BGJ398 will be dosed on a flat scale and not be adjusted to body weight or body surface area.

6.1.1 Dosing regimen

BGJ398 will be dosed on a flat scale of 125 mg (e.g., 1 x 100 mg and 1 x 25 mg capsules) once daily for the first 21 days of the 28-day cycle (3 weeks on, 1 week off in a cycle). A complete treatment cycle is defined as 28 days (refer to [Table 6-1](#)).

The patient must continue to meet all eligibility criteria on C1D1, as they did during the screening period. Refer to [Section 7.1](#) for more details.

Table 6-1 Dose and treatment schedule

Study treatment	Pharmaceutical form and route of administration	Dose	Frequency and/or Regimen
BGJ398	Capsule(s) for oral use	125 mg (administered as one 100 mg capsule and one 25 mg capsule)	Daily (3 weeks on, 1 week off schedule in 28-day cycles)

6.1.1.1 BGJ398 administration

[figure not shown]
The following general guidelines should be followed for administration.

- Patients should be instructed to take their daily dose of BGJ398 in the morning, at approximately the same time each day (24 ± 2 hour interval).
- BGJ398 should be administered in the fasted state, at least 1 hour before or 2 hours after a meal

- Phosphate binders should be given with meal (low phosphate diet), every day on days BGJ398 is given. No treatment with phosphate binders is needed during the BGJ398 off week in a cycle, unless the lab results indicate higher serum phosphorus levels that require continuous treatment with phosphate binders.
- BGJ398 should be taken with a large glass of water (~250 mL) and consumed over as short time as possible. Patients should be instructed to swallow the capsules whole and not to chew or crush them.
- If the patient forgets to take the scheduled dose in the morning, he/she should not take the dose more than 2 hours after the usual time and should continue treatment the next day. Any doses that are missed should be skipped altogether and should not be replaced or made up at the next scheduled dosing.
- Patients must avoid consumption of grapefruit, grapefruit juice, grapefruit hybrids, pomelos, pomegranates, star fruits, Seville oranges or juice within 7 days prior to the first dose of study medications, through the end of study participation. This is due to potential CYP3A4 interaction with the study medications. Orange juice is allowed.
- BGJ398 is characterized by pH-dependent solubility, and therefore, medicinal products that alter the pH of the upper gastro-intestinal tract may alter the solubility of both compounds, and limit bioavailability. These agents include, but are not limited to, proton-pump inhibitors (e.g., omeprazole), H2-antagonists (e.g., ranitidine) and antacids. Therefore, BGJ398 should be dosed at least 2 hours before or 10 hours after dosing with a gastric protection agent.
- If vomiting occurs during the course of treatment, no re-dosing of the patient is allowed before the next scheduled dose. The occurrence and frequency of any vomiting and/or diarrhea (or increased stool frequency) must be noted in the AEs section of the eCRF.
- At each visit, responsible site personnel will ensure that the appropriate dose of each study drug is administered and will provide the patient with the correct amount of study drug(s) for subsequent dosing. Patients will be instructed to return unused study drugs to the site at the end of each cycle.
- The investigator (or his/her designee) must instruct the patient to take BGJ398 exactly as prescribed. The patient should be instructed to contact the investigator (or his/her designee) if he/she is unable for any reason to take BGJ398 as prescribed. All dosages prescribed and dispensed to the patient, and all dose changes during the study, must be recorded on the Dosage Administration Record eCRF. Patients must be advised to bring their unused BGJ398 capsules/tablets to the investigative site at each visit.

6.1.2 Guidelines for continuation of treatment

Patients will be treated until disease progression (as assessed by investigator per RECIST 1.1 or appropriate hematologic response criteria or for patients with TIO diagnosis the recurrence or progression of disease or recurrence of abnormal metabolic parameters) or unacceptable toxicity death or discontinuation from study treatment for any other reason (e.g., withdrawal of consent, start of a new anti-neoplastic therapy or at the discretion of the investigator). Patients with TIO diagnosis that progress per RECIST but per investigator's assessment are receiving clinical benefit from treatment may remain on study upon approval from Novartis.

Guidance for continuation of study treatment in case of toxicity (e.g. dose delay and/or modification) is provided in [Section 6.3](#).

6.1.3 Treatment duration

Patients may continue treatment with the study drug until the patient experiences unacceptable toxicity that precludes further treatment, disease progression as assessed by the investigator (per RECIST 1.1 or appropriate hematological response assessment criteria or for patients with TIO diagnosis the recurrence or progression of disease or recurrence of abnormal metabolic parameters), death and/or treatment is discontinued due to any other reason. Patients with TIO diagnosis that progress per RECIST but per investigator's assessment are receiving clinical benefit from treatment may remain on study upon approval from Novartis. The reason for end of treatment (EOT) will be recorded in the corresponding eCRF.

6.2 Dose escalation guidelines

Not applicable.

6.3 Dose modifications

6.3.1 Dose modification and dose delay

For patients who do not tolerate the protocol-specified dosing schedule, dose adjustments are permitted in order to allow the patient to continue the study treatment. Any changes in BGJ398 administration must be recorded on the Dosage Administration Record eCRF.

BGJ398 dose modification guidelines are described in [Section 6.3.2](#). Any planned variance from these guidelines in the view of the patient safety must be previously discussed with the sponsor unless there is an urgent need for action.

All dose modifications, interruptions or discontinuations must be based on the worst preceding toxicity as graded by the NCI Clinical Toxicity Criteria for adverse events (NCI-CTCAE version 4.03). Once a dose has been reduced during a treatment cycle, re-escalation will not be permitted during any subsequent cycle.

If the administration of BGJ398 is interrupted for reasons other than toxicity, then treatment with the study drug may be resumed at the same dose. The same applies if the patient experienced an unacceptable toxicity not specifically described in [Table 6-3](#) or [Section 6.3.4](#), provided this toxicity resolved to \leq CTCAE grade 1, unless otherwise specified.

6.3.2 Permitted study treatment adjustments for BGJ398

For patients who are unable to tolerate the protocol-specified dosing schedule, dose reductions or interruptions are permitted to manage drug-related toxicities. For patients with TIO diagnosis additional dose reductions may be allowed upon Novartis approval.

- When dose reduction is necessary, the dose of BGJ398 may be reduced to 100 mg, QD.
- If an additional dose reduction is required, BGJ398 may be reduced to 75 mg, QD.
- Once the BGJ398 dose is reduced it cannot be re-escalated.
- All dose reductions should be based on the worst preceding toxicity.

- Patients are allowed only 2 dose reductions (to 100 mg and 75 mg) as specified in ([Table 6-2](#)).

Table 6-2 BGJ398 dose modifications

BGJ398 Dose Level	BGJ398 Dose
Starting dose level (0)	125 mg po QD (3 weeks on, 1 week off in a 28 day cycle)
Dose level – 1	100 mg po QD (3 weeks on, 1 week off in a 28 day cycle)
Dose level – 2	75 mg po QD (3 weeks on, 1 week off in a 28 day cycle)

- A third or subsequent reduction (to 50 mg, QD) in dose may be allowed if the patient is clearly benefiting from study treatment (i.e., stable disease, partial response, or complete response) but is experiencing adverse events that prevent continued treatment at the already reduced dose. For patients with TIO diagnosis without measureable/evaluable disease, the assessment criteria for additional dose reduction will be the tumor associated improvement of metabolic parameters. A third reduction or subsequent dose reduction requires approval from Novartis.

Patients whose treatment is interrupted or permanently discontinued due to an adverse event including abnormal laboratory values must be followed at least once a week for 4 weeks, and subsequently at 4-week intervals, until resolution or stabilization of the event, whichever comes first. The maximum time allowed for treatment interruption due to toxicity is 14 days (2 weeks) from the intended dosing day. If interruption is > 14 days, the patient must be discontinued from the study treatment. However, the patient will continue to be followed for toxicity. Dose interruptions should be reported on the appropriate Dosage Administration eCRF.

6.3.3 Criteria for interruption and re-initiation of BGJ398 treatment

If the administration of BGJ398 must be interrupted because of an unacceptable toxicity, BGJ398 dosing will be interrupted or modified according to rules described in [Table 6-3](#).

A patient who requires a dose interruption (regardless of the reason for the interruption) lasting >14 days (counting from the first day when a dose was missed) should discontinue the study treatment unless clearly demonstrating clinical benefit.

Table 6-3 BGJ398 related toxicity management guidelines

Worst Toxicity CTCAE v4.03 Grade (unless otherwise specified)	Recommended Dose Modifications any time during a cycle of therapy
Cardiac disorders	
Cardiac - Prolonged QTcF interval	
Grade 1 and 2 : QTcF \geq 481 msec and \leq 500 msec (asymptomatic)	
Maintain dose level of BGJ398
 
ECG (Electrocardiogram) assessments should be performed for 2 additional cycles at the same frequency as in cycle 1, or as clinically indicated
 
 • If ECG assessments show no QTcF \geq 481 msec, for subsequent cycles ECG monitoring will be performed as per visit schedule. • If ECG assessments are still abnormal (QTcF \geq 481 msec and \leq 500 msec), then ECG monitoring must continue at the same frequency as in cycle 1 for all subsequent cycles.
Grade 3 : QTcF $>$ 500 msec as identified on the ECG by the investigator	
 • Hold BGJ398. • Monitor patient with hourly ECGs until the QTcF has returned to baseline. • Perform further monitoring as clinically indicated. • Exclude other causes of QTcF prolongation such as hypokalemia, hypomagnesaemia and decreased blood oxygenation. • Patients should receive appropriate electrolyte replacement and should not receive further BGJ398 until electrolytes are documented to be within normal limits. • Once the QTcF prolongation has resolved and if the QTcF prolongation was confirmed by the central reader, patients may be re-treated at one lower dose level at the investigator's discretion • ECG assessments should be performed for 2 additional cycles at the same frequency as in cycle 1 or as clinically indicated 
 • If ECG assessments show no QTcF \geq 481 msec, for subsequent cycles ECG monitoring will be performed as per visit schedule. • If ECG assessments are still abnormal (QTcF \geq 481 msec and \leq 500 msec),

Worst Toxicity CTCAE v4.03 Grade (unless otherwise specified)	Recommended Dose Modifications any time during a cycle of therapy
	
then ECG monitoring must continue at the same frequency as in cycle 1 or as clinically indicated, for all subsequent cycles
 
 Patients who experience recurrent QTcF \geq 500msec after one dose reduction will be discontinued from study. 
NB: If ventricular arrhythmia or Torsades de Pointes is observed in a patient, he/she will be discontinued from the study.
 
Whenever QTcF $>$ 500msec is observed, a plasma sample for determination of BGJ398 concentration should be obtained with the time of sample collection noted.

Cardiac disorders - others Grade \geq 3, or congestive heart failure \geq 2	Discontinue patient from study treatment.
Investigations-Hematology	
ANC decreased (Neutropenia) Grade 3 (ANC $<$ 1.0 - $0.5 \times 10^9/L$)	Hold dose of BGJ398 until resolved to CTCAE Grade \leq 1 or baseline (repeat parameter at least twice a week and as indicated), then 
 If resolved within \leq 7 days, maintain dose level of BGJ398 If resolved within $>$ 7 days, \downarrow 1 dose level of BGJ398.
Grade 4 (ANC $<$ $0.5 \times 10^9/L$)	Hold dose until resolved to CTCAE Grade \leq 1 or baseline (repeat parameter at least twice a week and as indicated), then: 
 If resolved by \leq 7 days after suspending BGJ398, maintain dose level. If resolved by $>$ 7 days after suspending BGJ398, \downarrow 1 dose level.
Febrile neutropenia Grade 3 (ANC $<$ $1.0 \times 10^9/L$, single temperature of $>$ 38.3°C or a sustained temperature of \geq 38.0°C) Grade 4	Hold dose of BGJ398 until resolved to CTCAE Grade \leq 1, then 
 If resolved within \leq 7 days, \downarrow 1 dose level of BGJ398. If not resolved within 7 days discontinue patient from study drug treatment. Discontinue patient from study treatment.

Worst Toxicity CTCAE v4.03 Grade (unless otherwise specified)	Recommended Dose Modifications any time during a cycle of therapy
Hemoglobin Grade 3 (<8.0 mg/dL – 6.5 mg/dL) Grade 4 (< 6.5 mg/dL)	Hold dose of BGJ398 until resolved or corrected to CTCAE Grade ≤ 1 or baseline, then maintain dose level Hold dose of BGJ398 until resolved or corrected to CTCAE Grade ≤ 1 or baseline, then ↓ 1 dose level
Platelet count decreased (Thrombocytopenia) Grade 3 (PLT < 50 - 25 x 10 ⁹ /L) without bleeding Grade 3 (PLT < 50 - 25 x 10 ⁹ /L) with bleeding or Grade 4 (PLT < 25 x 10 ⁹ /L)	Hold dose of BGJ398 until resolved to CTCAE Grade ≤ 1 or baseline (repeat parameter at least twice a week and as indicated), then: 
 • If resolved within ≤ 7 days, maintain dose level of BGJ398. • If resolved within > 7 days, ↓ 1 dose level of BGJ398 Hold dose of BGJ398 until resolved to CTCAE Grade ≤ 1 or baseline (repeat parameter at least twice a week and as indicated), then ↓ 1 dose level
Investigations – Renal	
Serum creatinine Grade 1 Grade 2 Grade ≥ 3 or 4	Maintain dose level Omit dose until resolved to CTCAE Grade ≤ 1 or baseline, then: 
 • If resolved by ≤ 7 days after suspending BGJ398, maintain dose level. • If resolved by > 7 days after suspending BGJ398, ↓ 1 dose level. Omit dose and discontinue patient from study. If serum creatinine Grade ≥ 2 has been demonstrated in conjunction with hyperphosphatemia , serum creatinine levels must be repeated at least weekly until resolution, and 24-hour urine collection should be obtained as clinically indicated for total phosphate, calcium, protein, and creatinine clearance. Ultrasound examination of the kidneys should be performed as clinically indicated to evaluate de-novo calcifications until resolution or stabilization of creatinine.

Worst Toxicity CTCAE v4.03 Grade (unless otherwise specified)	Recommended Dose Modifications any time during a cycle of therapy
Investigations – Hepatic	
Blood bilirubin (patients with Gilbert Syndrome these dose modifications apply to changes in direct bilirubin only)	
Grade 2 for > 7 consecutive days	Hold dose of BGJ398 until resolved to CTCAE Grade \leq 1 or baseline (repeat parameter at least twice a week and as indicated), then: 
 • If resolved within \leq 7 days, maintain dose level of BGJ398. • If resolved within > 7 days, \downarrow 1 dose level of BGJ398.
Grade \geq 3	Omit dose until resolved to CTCAE Grade \leq 1 or baseline (repeat parameter at least twice a week and as indicated), then \downarrow 1 dose level.
Grade 4	Discontinue patient from study treatment. Patients with total bilirubin \geq Grade 1 (any duration) should have fractionation of bilirubin into total/direct or indirect/direct components and any additional work-up as clinically indicated by these results. Follow-up of hyperbilirubinemia should proceed as per the guidelines mentioned above, irrespective of the results of fractionation.
AST or ALT	
Grade 3	Hold dose of BGJ398 until resolved to CTCAE Grade \leq 1 or baseline (repeat parameter at least twice a week and as indicated), then: 
 • If resolved within \leq 7 days, maintain dose level of BGJ398. • If resolved within > 7 days, \downarrow 1 dose level of BGJ398. Discontinue patient from study treatment.
Grade 4	
AST or ALT and Bilirubin	
AST or ALT $>$ 3.0 – 5.0 x ULN and total bilirubin $>$ 2.0 x ULN without liver metastasis or evidence of disease progression in the liver	Hold dose of BGJ398 until resolved to CTCAE Grade \leq 1 
 • If resolved within \leq 7 days, \downarrow 1 dose level of BGJ398. • If resolved within > 7 days, discontinue patient from study treatment. Discontinue patient from study treatment.
AST or ALT $>$ 5.0 x ULN and total bilirubin $>$ 2.0 x ULN	

Worst Toxicity CTCAE v4.03 Grade (unless otherwise specified)	Recommended Dose Modifications any time during a cycle of therapy
Laboratory / Metabolic disorders	
Asymptomatic amylase and/or lipase elevation	
Grade 3 (> 2.0 - 5.0 x ULN)	
 • Hold dose of BGJ398 until resolved to CTCAE Grade ≤ 2. • ↓ 1 dose level of BGJ398
Grade 4 (> 5.0 x ULN)	
For recurrent grade 3 asymptomatic lipase or amylase elevation despite dose reduction, drug should be held and continuation of therapy should be discussed with the medical monitor following resolution to ≤ grade 2.
 
For any grade 4 asymptomatic lipase or amylase elevation, drug should be held and continuation of therapy should be discussed with the medical monitor following resolution to ≤ grade 2.

	
Note: A CT scan or other imaging study to assess the pancreas, liver, and gallbladder should be performed as clinically indicated within 1 week of the first occurrence of any CTCAE ≥ Grade 3 amylase and/or lipase.

Grade 4 (> 5.0 x ULN)	Discontinue patient from study treatment
Hyperphosphatemia	Hold BGJ398 dose until resolved to serum phosphorus ≤ 5.5 mg/dL:
	Restart BGJ398 at the same dose level with maximal phosphate binder dosing if the patient did not receive maximal phosphate binder dosing for serum phosphorus > 7.0 mg/dL for > 7 days.
	Reduce one dose level of BGJ398 if the patient had received maximal phosphate lowering therapy for serum phosphorus > 7.0 mg/dL for > 7 days Or if patient had a one-time serum phosphorus of > 9.0 mg/dL. Restart BGJ398 with maximal phosphate binder dosing.
	It is recommended that phosphate binder dosing continues during BGJ398 dose interruptions for hyperphosphatemia and that serum phosphorus values be monitored frequently, e.g. every 2-3 days.
	Phosphate binder dosing should be held during the week off BGJ398 therapy each cycle (Days 22-28) for “3 weeks on / 1 week off” dosing regimen and during BGJ398 dose interruptions for non-hyperphosphatemia adverse events.

Worst Toxicity CTCAE v4.03 Grade (unless otherwise specified)	Recommended Dose Modifications any time during a cycle of therapy
Hypercalcemia Serum calcium grade 2	Hold BGJ398 dose until resolved to grade 1 or baseline: 
• if resolved within \leq 7 days after suspending BGJ398, maintain dose level• if resolved within $>$ 7 days after suspending BGJ398, \downarrow 1 dose level Discontinue patient from the study
Serum calcium \geq grade 3	
Nervous system disorders	
Neurotoxicity Grade 2	Omit dose of BGJ398 until resolved to CTCAE Grade \leq 1, then \downarrow 1 dose level of BGJ398
Grade \geq 3	Discontinue patient from study drug treatment
GI disorders	
Pancreatitis Grade \geq 2	Discontinue patient from study drug treatment
Diarrhea Grade 1	Maintain dose level of BGJ398, initiate anti-diarrheal treatment
Grade 2	
• Hold dose of BGJ398 until resolved to CTCAE Grade \leq 1• Optimize anti-diarrheal treatment, maintain dose level of BGJ398.• For reoccurrence of diarrhea CTCAE Grade 2, hold dose of BGJ398 until resolved to CTCAE Grade \leq 1, \downarrow BGJ398 by 1 dose level• Hold dose of BGJ398 until resolved to CTCAE Grade \leq 1• Optimize anti-diarrheal treatment• \downarrow BGJ398 by 1 dose level
Grade 3	
• For reoccurrence of diarrhea CTCAE Grade 3, despite optimal anti-diarrheal treatment, discontinue patient from study treatment.

Worst Toxicity CTCAE v4.03 Grade (unless otherwise specified)	Recommended Dose Modifications any time during a cycle of therapy
Grade 4	
Discontinue patient from study treatment.
 
Note: Antidiarrheal medication is recommended at the first sign of abdominal cramping, loose stools or overt diarrhea

Vomiting Grade 2 not controlled by optimal anti-emetic therapy Grade 3 not controlled by optimal anti-emetic therapy or Grade 4	
Hold BGJ398 doses until \leq grade 1, \downarrow 1 dose level
 
Discontinue patient from study

Eye Disorders (confirmed by ophthalmologic examination)	
Retinal and Corneal disorders Grade 2 CSR and CSR-like events, Grade 2 Corneal disorder Grade 3 CSR and CSR-like events and any other grade 3 eye disorders \geq grade 1 retinal vein occlusion, grade 4 CSR and CSR-like events, and grade 4 other eye disorders	
Hold BGJ398 until resolved to \leq grade 1 and continue ophthalmologic evaluation
 
 • If resolved within \leq 14 days, \downarrow BGJ398 by 1 dose level • If resolved within $>$ 14 days, discontinue BGJ398 
Hold BGJ398 until resolved to grade \leq 1.
 
 • If resolved within \leq 14 days, \downarrow BGJ398 by 1 dose level • If resolved within $>$ 14 days, discontinue BGJ398 
Discontinue BGJ398

Other ocular/visual toxicity \geq grade 3	
Hold BGJ398 until resolution to \leq grade 1
 
If resolution within \leq 14 days, \downarrow 1 dose level, otherwise discontinue BGJ398

General disorders	
Fatigue Grade 3	
Hold dose of BGJ398 until resolved to CTCAE Grade \leq 1
 
 • If resolved within \leq 7 days, maintain dose level of BGJ398. • If resolved within $>$ 7 days, discontinue patient from study treatment.

Worst Toxicity CTCAE v4.03 Grade (unless otherwise specified)	Recommended Dose Modifications any time during a cycle of therapy
Other clinically significant AEs	
Grade 3	Hold dose of BGJ398 until resolved to CTCAE Grade \leq 1, then \downarrow 1 dose level of BGJ398.
Grade 4	Discontinue patient from study treatment.
All dose modifications should be based on the worst preceding toxicity. Once a dose reduction has occurred, no dose increases can be subsequently implemented. Patients who require more than two dose reductions of BGJ398 will be generally discontinued from study drug treatment.	

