7.1.3.2 Criteria for premature patient withdrawal (EOT phase completion)

Patients **may** voluntarily withdraw from the study or be dropped from it at the discretion of the investigator or by the sponsor at any time.

Premature patient withdrawal refers to the point/time when the patient exits from the study treatment prior to the planned completion of all study treatment administration and/or assessments; at this time, all study drug treatment is discontinued and no further assessments are planned, unless the patient will be followed for progression and/or survival.

Patients may be withdrawn from the study treatment if any of the following occur:

- Adverse Event
- Lost to follow-up
- Non-compliance with study treatment
- Physician decision
- Pregnancy
- Progressive Disease
- Protocol deviation
- Study terminated by sponsor
- Subject/guardian decision
- Death
- In addition to the general withdrawal criteria, the following **study specific criteria** will also require study treatment discontinuation:
 - Adjustments to study treatment that result in discontinuation. Please refer to [Section 6.3](#).
 - Use of prohibited medication. Please refer to [Section 6.4.3](#).

- Interruption of study treatment for > 14 days, regardless of reason, from the intended day of the next scheduled dose

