6.1 Clinical Benefit Rate (CBR)

Clinical benefit is determined by investigator assessment for each tumor assessment and is defined as responses of CR or PR or SD \geq 16 weeks. For subjects with TIO diagnosis without measureable/evaluable disease, the following criteria will be used to determine the assessment at 16 weeks:

- the tumor associated changes of metabolic parameters: plasma level of FGF23 < or =180 RU/mL; and inorganic phosphorous, calcium, and 1-25-dihydroxy vitamin D greater than the lower limit of normal (LLN) (20%); and
- without requirement of supplementation therapy for at least the preceding cycle of the 16 week assessment.

Subjects with TIO diagnosis, but having known underlying tumor/disease type, their tumor response summaries will be treated same as for subjects with the same underlying tumor type.

In addition to tumor-specific measurements (e.g., radiological assessment of tumor response for solid tumors), progressive disease will also be considered when it was indicated either as a reason based on clinical assessment for the study treatment discontinuation or as a cause of on-treatment death. CR and PR (for solid tumors) require a confirmation that is at least a minimum of 4 weeks after the initial observation of response. Subjects who had confirmed CR/PR or SD prior to 16 weeks, but discontinued prior to 16 weeks for reasons other than

progressive disease, will have their clinical benefit defined as non-evaluable; subjects who had confirmed CR/PR or SD prior to 16 weeks, but progressed prior to 16 weeks, will be considered as not achieving clinical benefit; subjects who had CR/PR/SD occurred prior to 16 weeks, but progressed at or after 16 weeks without evidence of CR/PR/SD at or after 16 weeks, will also be considered as not achieving clinical benefit. CBR will be analyzed by comparing achieved CBR with a historical control rate of each tumor type, and if there is at least 90% probability that the response rate in a tumor type exceeds the historical rate, then the tumor type will be considered a success; it will be considered as promising if the probability is between 80% and 90%. Details for the analyses of CBR are located in Section [Error! Reference source not found.](#)

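### The protocol gives opposite instructions for a benefiting patient whose treatment interruption passes 14 days, and before week 16 the choice also decides how the SAP can classify clinical benefit

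*Protocol*

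**What the plan says.** Three sections of the protocol govern a long interruption.

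- Section 6.3.2, on interruptions for toxicity: "The maximum time allowed for treatment interruption due to toxicity is 14 days (2 weeks) from the intended dosing day". It continues: "If interruption is > 14 days, the patient must be discontinued from the study treatment".
- Section 7.1.3.2 lists study-specific criteria that "will also require study treatment discontinuation". One of them is "Interruption of study treatment for > 14 days, regardless of reason, from the intended day of the next scheduled dose".
- Section 6.3.3 applies to an interruption of the same length whatever its cause, counted from the first missed dose. It says the patient "should discontinue the study treatment unless clearly demonstrating clinical benefit".

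SAP 6.1 deals with subjects who had confirmed CR/PR or SD before week 16 but "discontinued prior to 16 weeks for reasons other than" progressive disease. They "will have their clinical benefit defined as non-evaluable". Protocol 7.1.4.2 provides no efficacy follow-up once treatment stops, so a later scan is not available to settle the patient's status.

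**The concern.** This is a treatment-stopping rule, and for one kind of patient (over the limit, judged to be benefiting) the current text both requires and waives discontinuation. Section 12 of the protocol allows no authorised deviations, so a site that uses the 6.3.3 exception is in breach of 7.1.3.2.

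The exception is also loosely bounded. Section 6.3.3 neither defines clinical benefit nor asks for sponsor approval. Section 6.3.2 does both for a third dose reduction.

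The statistical stake is that the exception depends on benefit as judged by the investigator, in an open-label trial whose primary endpoint is also assessed locally. Whether a patient's week-16 status can be observed may therefore depend on how well the patient seems to be doing.

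**Working it through.** No figure in the plan rests on this rule, so there is nothing to reproduce. The check is a comparison of texts, followed by a sensitivity illustration.

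**1. The rules side by side**

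| Protocol section | Scope | Count starts | Consequence after 14 days | Exception |
|---|---|---|---|---|
| 6.3.2 | toxicity | intended dosing day | must stop | none |
| 6.3.3 | any reason | first missed dose | should stop | clear clinical benefit |
| 7.1.3.2 | any reason | intended day of next scheduled dose | stop required | none |

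Scope does not remove the conflict. Section 6.3.2 is limited to toxicity, but 6.3.3 and 7.1.3.2 both cover any reason and disagree for a benefiting patient.

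**2. The count**

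A dose is missed on the day it was due, so the three starts can be read as the same day. What is unstated is whether off-week days count. Take a patient who misses doses from day 15 and resumes on day 2 of the next cycle:

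- Calendar gap: days 15 to 28 (14 days) plus day 1 (1 day) = 15 days, which is over the limit.
- Doses missed: days 15 to 21 (7 doses) plus day 1 (1 dose) = 8 doses.

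Sites could reasonably disagree on whether this patient passed 14 days.

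**3. The path to the primary endpoint**

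- Under 6.3.2 or 7.1.3.2, a patient with confirmed CR/PR or SD who passes the limit before week 16 is stopped. Under SAP 6.1, clinical benefit is then non-evaluable.
- Under 6.3.3, the same patient may continue, be assessed at week 16 and count as benefit or no benefit.
- The first scheduled disease assessment is at week 8, so the relevant window is roughly week 8 to week 16. Later interruptions do not affect CBR evaluability.
- Protocol 10.1.1 uses the FAS (all dosed patients) for efficacy, and 10.4.4 allows no imputation. Neither document says whether a non-evaluable patient leaves the CBR denominator or stays in it as a non-success.

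**4. Illustration with assumed counts**

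Inputs from Appendix R and SAP 10: θ ~ N(μ, τ²), μ ~ N(0, 1.82), τ² ~ IG(3, 0.5). The control rate is R = 0.45 (HNSCC) or 0.47 (bladder, ovarian). The 0.90 final success threshold is from Protocol 10.4.3 and SAP 6.1. Assumed: 10 patients dosed, 6 benefits among the other 9, and one patient with SD who passes the limit before week 16. The quantity is Pr(π > R | x of n) for one cohort without borrowing, by Monte Carlo. Ranges cover reading 1.82 as a variance or as an SD.

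| Handling of the one patient | x/n | R = 0.45 | R = 0.47 |
|---|---|---|---|
| stopped, removed from denominator | 6/9 | 0.886–0.896 | 0.864–0.875 |
| continues, benefit at week 16 | 7/10 | 0.931–0.939 | 0.914–0.923 |
| stopped and counted as failure, or continues without benefit | 6/10 | 0.810–0.819 | 0.778–0.787 |

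In this example one patient moves the cohort across 0.90. At R = 0.47 the handling also decides whether the cohort reaches the 0.80 bound for a promising result.

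**The case against.** The strongest reply is that the effect on the endpoint is small and the wording loose rather than harmful. Much of this stands.

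- The three starts can be read as one day, so a reader who infers that they demonstrably give different dates goes beyond the text. Only the treatment of the off week is shown to be open.
- Some toxicities in Table 6-3 have their own stop rule without a benefit exception: eye disorders not resolved within 14 days, and grade 3 fatigue or febrile neutropenia not resolved within 7. The conflict does not reach those cases.
- A reader might infer from Protocol 1.2.1.2.1 that long interruptions are common: 43% of patients on continuous dosing had cycle 1 interruptions, and 16% on the 3-on/1-off schedule had cycle 1 interruptions or reductions. Those figures do not give duration, and cycle 1 ends before the first scheduled scan. The only duration given is a phase I median of 7 days, half the limit, and it too comes from a different setting.
- The illustration uses invented counts and no borrowing. Comparing x/9 with (x+1)/10 for every x, only x = 6 crosses 0.90, and one extra success from any cause would do the same.
- SAP 2 says most subjects had already stopped treatment, so rewording would change the management of few patients.

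None of this removes the direct conflict between 6.3.3 and 7.1.3.2, or between 6.3.3 and 6.3.2 for toxicity. Nor does it supply the missing CBR counting rule.

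**Conclusion.** The contradiction is in current protocol text and must be reconciled because sites have opposite instructions under a stopping rule. That ground is sufficient without any claim about bias in CBR.

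The link to the primary endpoint is real but narrow. It needs a patient with confirmed CR/PR or SD, an interruption over 14 days, and the limit passed before week 16. Its frequency is not given and cannot be computed from the documents. The posterior values show only that a small cohort can be sensitive to one patient; they are not an estimate of bias.

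A reader might infer that every patient stopped before week 16 without progression drops out of an evaluable set. The documents do not support that. SAP 6.1 applies the non-evaluable class only to subjects with confirmed CR/PR or SD, no such analysis set is defined for CBR, and the denominator is left unstated. Non-evaluability also follows from any other early stop without progression, so it is not created by this conflict. The conflict only makes it depend on which section a site follows.

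**What to change.** The sponsor should reconcile Protocol 6.3.2, 6.3.3 and 7.1.3.2 to a single rule, with one defined start for the 14 days and an explicit statement on whether off-week days count. This review takes no view on which rule or count is right. If an exception based on benefit remains, the protocol should say how benefit is determined and documented.

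The SAP should state how patients discontinued under the rule before week 16 enter the CBR numerator and denominator. That statement remains useful even if the protocol wording comes too late for most patients, because it also governs those already treated.

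The cost is a clarifying protocol amendment with its IRB/IEC approval and a few sentences in SAP 6.1. No new data collection is needed: dose interruptions are already recorded on the dosage administration eCRF.
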